CE-GAX001-01

V4.0

CR: 144

Date: _____

HidraWear AX HS Study Protocol ID: CE-GAX-001-01 V4 NCT:04449354

Initial Release Date: 18th October 2019

Signed: _____

Sponsor Name: HidraMed Solutions Ltd.

Sponsor Address: [name]

Date:

HidraMed Solutions Ltd.

Signed: _____

Chief Investigator

This document contains confidential and proprietary information and may not be copied or reproduced in whole or part without the written permission of HidraMed Solutions Ltd.

CE-GAX001-01

V4.0

CR: 144

Clinical Agreement Signature Log

I, the undersigned, have read and understand the Clinical Investigation Plan (CIP), and agree to conduct the investigation as stipulated.

The CIP, the Investigator Agreements and any additional information provided by the sponsor will serve as a basis for co-operation in the study.

I will provide copies of the CIP and all pertinent information to all individuals responsible to me who assist in the conduct of this study. I will discuss this material with them to ensure they are fully informed regarding the device and the conduct of the study.

I will use only the informed consent form approved by the Ethics Committee (EC) and will fulfil all responsibilities for submitting pertinent information to the EC.

Principal Investigator:		
Signature	Date	

Name, address and professional position of Principal Investigator:

[name]. Consultant in Rheumatology and General Medicine.

Hermitage Medical Clinic, [name]

CE-GAX001-01

V4.0

CR: 144

Clinical Investigation Summary

Title	HidraWear AX Pilot Study			
Investigational Product	HidraWear AX			
Introduction	The product, HidraWear AX is and adhesive free wound dressing system for the every day home care of Hidradenitis Suppurativa (HS), a debilitating disease of the skin for which there are limited wound dressing products.			
	This is a study to assess the use HidraWear Ax vs current product and method of use.			
Study Objectives:				
	The objective is to evaluate the ease of use of Hidrawear AX compared to the subject's existing product use in 23 subjects with HS (Hidradenitis Suppurativa).			
	Secondary objectives are to evaluate if Hidrawear AX:			
	Is comfortable			
	Improves quality of life			
	Faster to use than the subject's existing product			
	Reduces dressing related pain			
	Secure dressing retention			
Study Design:	Sample size: 23			
	Female, over 18, presenting with HS of the axilla			
	Study Duration: 9 months - from when the study opens to enrolment until completion of data analyses			
	Subject participation duration: 3 weeks			
Sample size and study	Sample size: 23			
duration:	Female, over 18, presenting with HS of the axilla			
	Study Duration: 9 months - from when the study opens to enrolment until completion of data analyses			
	Subject participation duration: 3 weeks			

CR: 144

	In order to be eligible to participate in this study, an individual must meet all of the following criteria:				
	3				
	1. Provision of signed and dated informed consent form in English.				
	2. Stated willingness to comply with all study procedures and availability for the duration of the study				
	3. Female, aged >18				
	4. Diagnosed with Hidradenitis Suppurativa				
	5. Hidradenitis Suppurativa affecting the axilla				
	6. Exuding lesion that requires wound dressings				
	Exclusion Criteria:				
	1. Recent surgery <3 months in axilla				
1	2. Psoriasis, Dermatitis or skin conditions/rash other than Hidradenitis Suppurativa on or near affected area				
	3. Pregnancy or lactation				
	4. Known allergic reactions to components of Hidrawear AX				
Primary Performance					
Endneinter	Primary outcome measure:				
	Subjects own product use (Day 0) vs Hidramed (Day 21)				
	• Ease of Use Day 21 vs Day 0				
Secondary	Secondary outcome measures:				
Performance	 Ease of Use Day 21 vs Day 0 Comfort, measured 				
Endpoints:	on a 5-point scale Day 21 vs Day 0				
	 Visual Pain Analogue Scale Day 21 vs Day 0 				
	Time Day 21 vs Day 0				
	 Additional equipment used – mirror, scissors etc 				
	Could dressing be applied without raising arms over head				
	Necessity to stretch/contort body to apply dressing				
	Did subject need assistance				
	9 months - from when the study opens to enrolment until completion of data analyses.				
	Subject participation: 22 days, Visit day 0, and day 21.				

CE-GAX001-01

V4.0

CR: 144

2 INTRODUCTION

Hidradenitis Suppurativa (HS) is a debilitating lifelong condition characterized by painful nodules and lesions localized mainly in the inverse body areas, such as the axillae and groin [1]. These lesions are typically fluid filled and require regular wound dressings. People with HS live in dressings and bandages.

Hidradenitis Suppurativa

- Presents after puberty with an average diagnosis pathway of 8 years [2]
- Is frequently misdiagnosed due to lack of clinical awareness [3]
- Causes deep seated, painful skin lesions, tunneling tracts and wounds
- Affects the armpits, groin, thigh and buttocks
- Causes irreversible skin damage
- Causes high levels of subject pain, distress and despair [4]
- Subjects at higher risk of anxiety, depression and suicide [5]

People living with HS are tending to their lesions widely unaided. The majority of subjects, unless referred to a wound clinic, are self-managing. [6]

There are no recommended products or guidelines on how to manage HS lesions and there are no wound dressings that are suitable for use on the armpit. Current dressings often leak, move or fall off and the constant application and removal of adhesives to the skin further irritates and damages the affected area. Subjects are doing on average 3-4 dressing changes per day, using products that are not fit for purpose.

2.1 Description of the Investigational Device

HidraMed Solutions has developed an adhesive free wound dressing fixation device for people living with Hidradenitis Suppurativa (HS), a chronic and debilitating disease which causes non-healing lesions of the skin, mainly in the armpit, groin, thigh and buttocks - Hidrawear AX, designed to make dressing changes quick and easy for subjects.

The Hidrawear AX is designed to improve the wound care management for HS and chronic wound subjects. The unique features of the product completely remove the use of adhesives on the skin. Designed by a patient, for patients, Hidrawear AX provides comfort, ease of use and effective care for the every-day management of HS lesions.

The 3- part system is comprised of

- 1. The investigational device: the Hidrawear AX: A washable garment
- 2. An off-the-shelf dressing
- 3. An off-the-shelf mechanism to attach the dressing to the Hidrawear AX, such as a fastener supplied with the dressing or medical tape

The body conforming garment acts as a second skin and incorporates largely perforated panels over wound affected areas, minimising skin contact and aerating the area. The main function of the perforated is to act as a retaining device for the wound pads.

[figure not shown]

[figure not shown]
CE-GAX001-01

V4.0

CR: 144

The garment facilitates easy insertion, removal, precise positioning and adjustment of a non-adhesive wound dressing onto the effected wound space. The perforated section of the garment sits on the outer surface of the dressing providing provisional fixation. Next, an outer patch is placed on the outside of the garment on the footprint of the dressing. Through a hook and loop mechanism the dressing is now fully secured in place. It is designed so that quick, precise and pain free dressing changes can be achieved in less than 15 seconds

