2.4 Contraindications and Warnings

A full list of contraindications and warnings are provided in the IFU supplied with the device.

Contraindications: Known allergies to materials specified

Warnings: Do not use if you have known allergies to materials specified.

Warnings

- 1. The garment is not a wound dressing wound(s) should be fully covered by dressing(s).
- 2. If any unexpected discomfort or wound irritation occurs, please consult your doctor or nurse.
- 3. Do not use, if you have a known allergy or sensitivity to materials listed.

CE-GAX001-01

V4.0

CR: 144

Potential side effects: Dermatitis, infection and skin irritation or skin abrasion.

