4 RISKS AND BENEFITS

4.1.1 Risk Analysis

- Hidradenitis Suppurativa wounds can sometimes be colonised by non-pathogenic bacteria, and may appear to be infected. This is not a true infection. However, subjects will examined by research nurse to assess the wound and will be asked to record their temperature during the study to monitor for signs of infection. There will be a registered nurse overseeing all subject interactions and demonstrations to ensure the safety of subjects
- Garment could cause discomfort to the subject. In the case of any discomfort the subject is requested to remove the wound care product
- There is also a minor concern re allergies to certain materials and this will be included in the PIL and will be an exclusion criteria

Risk assessment for Hidramed vs Standard Adhesive dressing.

Risk level and likelihood rated 1-5, 1 being the lowest and 5 being the highest.

Hidrawear AX Garment

Risk	Cause	Level of Risk	Likelihood of Risk	Control
Skin Irritation	Allergic to garment	1	1	Discontinue use immediately
Unnecessary Pain	Difficult dressing site			Use product as instructed exactly.
				Discontinue use immediately
Subject distress and embarrassment	Dressing leaking or falling off.	1	1	Use product as instructed exactly
Physical contamination of wound	Thread or fibres from product retained in wound	1	1	Selected bonded fabric that does not fray/produce fibres.
				Users instructed to carry out daily visual inspection of wound.
				Discontinue use immediately

CE-GAX001-01

V4.0

CR: 144

Dressing Supplied During Study

Risk	Cause	Level of Risk	Likelihood of Risk	Control
Skin Irritation	Allergic to dressings	1	1	Discontinue use immediately
Localised infection	Misuse of dressings	3	1	Follow user instructions exactly. Discontinue use immediately
Septicemia	Misuse of dressings	5	1	Follow user instructions exactly. Discontinue use immediately
				Monitor temperature twice daily during pilot period.
Subject distress and embarrassment	Dressing leaking or falling off.	1	1	Use product as instructed exactly

Standard Adhesive Dressing

Risk	Cause	Level of Risk	Likelihood of risk	Control
Skin Irritation	Allergic to or reaction to adhesive in dressing	1	3	Discontinue Use immediately
Localised infection	Misuse of dressings	3	3	N/A user instructions do not specify
Septicemia	Misuse of dressings	5	1	N/A user instructions do not specify
Unnecessary pain	Difficult dressing site, Adhesive damage to skin	5	4	N/A

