4.3 Adverse Device Effects

Materials selected are designed for contact with the skin and all use of adhesives on the skin have been removed so the likelihood of adverse effects due to using the device is low. However, there is a slight possibility of skin irritation, infection and pain due to misuse of the device. See table in section 4.1.1

In all instances of adverse effects, subjects must cease using the device immediately and make contact with research nurse for further instruction.

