4.6 Steps to be Taken to Control or Mitigate Risks

Users will be assessed by a Research Team member to establish that no infection is present in the wound site on enrolment and assessment.

Subjects will be asked to measure and record their temperature daily and to contact nurse support if there is an elevation in temperature.

If subjects record a pyrexia greater than 38 degrees. The Subject will contact the Research team where it will be recorded. Subject will be asked to recheck temperature following 1 hour without temperature reducing medication (paracetamol ibuprofen et). If pyrexia persists, subject will be directed to attend GP for immediate follow up and the use of the study device will be stopped.

Research nurse to assess whether pyrexia is device related.

If it is not device related, a telephone contact log is to be filled in and reported to the sponsor.

[figure not shown]
If it is device related, an adverse is to be recorded and reported to sponsor

CE-GAX001-01

V4.0

CR: 144

Process Flow for Pyrexia >38 Degrees

The dressing used in this study is provided sterile.

The fastener used in this study is used externally and does not touch the skin during use. Material base and Velcro is medical grade.

The dressing and fastener will be CE marked by the legal manufacturer (Planet Medical Products Co. Ltd., China). The manufacturer is ISO13485 certified.

Hidramed AX fabric is an OEKO-TEX® certified material. The Hidramed AX full produced garment has been evaluated in accordance with ISO 10993 and it is biocompatible for its intended use. Verification and validation testing will be performed to evaluate the design of the garment. Hidramed Solutions will CE mark the device in accordance with the medical device directive 93/42/EEC.

CE-GAX001-01

V4.0

CR: 144

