15.2 Definition: Adverse Device Effect (ADE)

An Adverse Device Effect (ADE) is defined as an adverse event related to the use of an investigational medical device resulting from insufficient or inadequate instructions for use, deployment, implantation, installation, operation, any malfunction, user error, or intentional misuse of the investigational medical device

Subjects will be fully trained on how to use the device and be provided with instructions for use. Subjects can contact research nurse at any time if unsure, and can send daily comments to the researcher through daily check ins.

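### The protocol defines the investigational device as the garment alone and does not say whether harm from the supplied dressing or fastener counts as device related

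*Combined protocol and SAP*

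**What the plan says.** Section 2.1 lists three parts. The first is "The investigational device: the Hidrawear AX: A washable garment". The other two are "An off-the-shelf dressing" and "An off-the-shelf mechanism to attach the dressing to the Hidrawear AX, such as a fastener supplied with the dressing or medical tape". Neither of these is called investigational. Section 12 says that subjects receive garments and three weeks of dressings. The synopsis uses a wider description and introduces HidraWear AX as a dressing system.

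The risk analysis in 4.1.1 has separate tables for the garment and for the "Dressing Supplied During Study", and a third for standard adhesive dressings. Section 2.4 gives "Potential side effects: Dermatitis, infection and skin irritation or skin abrasion". Section 4.3, on adverse device effects, says "there is a slight possibility of skin irritation, infection and pain due to misuse of the device. See table in section 4.1.1".

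Section 4.6 deals with fever above 38 degrees: "Research nurse to assess whether pyrexia is device related". If the answer is no, a telephone contact log is completed and sent to the sponsor. If it is yes, an adverse event is recorded and reported. Section 15.2 describes an adverse device effect as "defined as an adverse event related to the use of an investigational medical device". Section 15.5 builds the serious category on that definition. Section 15.1 defines an adverse event regardless of its relation to the device, and 15.6 says that all adverse events are captured.

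**The concern.** The boundary of the product differs between benefit and harm. On the Day 21 form, subjects rate HidraWear AX for ease, time, comfort, pain and confidence that it will not leak or move. Those ratings depend on the dressing and fastener as much as on the garment. Relatedness, in contrast, is judged against a device that 2.1 limits to the garment.

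Two assessors could therefore classify the same event differently. Suppose that a subject develops a fever from a wound infection linked to the supplied dressing. One assessor follows 2.1 and the 4.1.1 tables, attributes the event to the dressing, and answers that it is not device related. Another follows 4.3 and answers that it is. The answer decides whether the event enters the adverse device effect category and, under 4.6, whether an adverse event record is made at all. It also bears on the safety evaluation promised in 3.4 and on 16.1, where unanticipated device effects are a ground for suspending the study. Temperature is taken to watch for infection (4.1.1), so this route carries the study's main infection signal.

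**Working it through.** The plan states no figure on this point, so there is none to reproduce. The check is mainly a comparison of sections.

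**1. What counts as the device.** Section 2.1 says the garment. Section 4.5 agrees, describing the study as an assessment of the garment. The synopsis says a system. No section says which description governs causality.

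**2. Where infection is listed for the study products in 4.1.1.**

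| Table | Rows | Infection or septicaemia rows |
|---|---|---|
| Garment | 4: irritation, pain, distress, fibre contamination | 0 |
| Supplied dressing | 4: irritation, localised infection, septicaemia, distress | 2 (risk levels 3 and 5) |

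Both infection rows give misuse of dressings as the cause. Section 4.3 attributes infection to misuse of the device and refers the reader to 4.1.1, where the garment table has no such row. Sections 2.4 and 4.3 therefore do not match the garment table.

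**3. Whether dressing or fastener harm is device related.** Section 15.2 refers to use of an investigational medical device and names neither component. Section 15.5 does not repeat that phrase; it inherits the boundary through the term adverse device effect. Section 4.6 asks the question without defining it. The fastener has no risk table, and 4.6 says it does not touch the skin, so for the fastener the point rests on 2.1 and 15.2 alone.

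**4. What follows from the answer.** Under 4.6, a fever judged unrelated leads to a telephone log. Under 15.1 and 15.6, relatedness has no bearing on whether an event is an adverse event or is captured. These sections conflict.

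**5. Scale.** The inputs are n = 23 (7.2) and an assumed x = 0 or 1 device-related events. The exact (Clopper-Pearson) 95% limits are: lower = Beta(0.025; x, n − x + 1), upper = Beta(0.975; x + 1, n − x).

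- Counted as related, x = 1: 1/23 = 4.3%; lower = 1 − 0.975^(1/23) = 0.1%; upper = Beta(0.975; 2, 22) = 21.9%.
- Counted as unrelated, x = 0: 0%; lower = 0; upper = 1 − 0.025^(1/23) = 14.8%.

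If the 6 anticipated drop-outs (7.4) left 23 − 6 = 17 subjects, the same formulas give 1/17 = 5.9% (0.1 to 28.7%) against 0% (0 to 19.5%).

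**The case against.** Treating the garment separately is partly a legitimate choice. The other parts are off the shelf and are to be CE marked by another manufacturer (4.6). Section 3.4 says that the clinical effect of the wound pad is not assessed. The dressing's risks are disclosed in their own table. All of this stands, but it does not settle how relatedness is to be judged.

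A reader might infer four stronger things that the documents do not support.

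- *That the protocol lists infection and septicaemia only under the supplied dressing.* Both are also in the standard adhesive dressing table, and 2.4 and 4.3 name infection. The statement holds only within the two study-product tables.
- *That harm from the dressing must be classed as unrelated.* Section 15.2 covers use of the device, including user error and inadequate instructions, and the garment exists to hold a dressing (2.3). Section 4.3 can be read as treating the dressing rows as device effects. The text is silent on the question and excludes nothing.
- *That such harms disappear.* Sections 15.1 and 15.6 capture adverse events whatever the cause, 15.4 does the same for serious events, and even the telephone log reaches the sponsor. The exception is the conflict with the 4.6 route.
- *That a planned device-effect rate will be wrong.* Neither section 7 nor 15.6 specifies such a count, a denominator or a safety analysis.

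Procedure QP025 and the instructions for use are outside the document, and the 4.6 flow chart could not be read. A field for the suspected component may already exist.

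**Conclusion.** The point holds as an ambiguity in the causality boundary together with two internal inconsistencies. Harm from the supplied dressing or fastener may be left out of the adverse device effect category because the protocol does not say where it belongs. The garment risk table does not match 2.4 and 4.3. The recording route in 4.6 conflicts with 15.1 and 15.6.

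Misclassification is possible but not prescribed, and its frequency cannot be estimated from the documents. The 4.3% against 0% comparison rests on one assumed event among 23 subjects and shows scale only. In a study of this size, a single judgement separates an observed device effect from none. The wide and overlapping intervals mean that neither result would establish a rate. The change is worth making before enrolment, because the suspected component may be hard to reconstruct afterwards.

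**What to change.** - State in 2.1, 4.6 and 15.2 that, for causality, device related means related to any supplied component: garment, dressing, fastener or tape. Section 15.5 then follows through 15.2.
- Add a field for the suspected component to the event record, so that attribution to the garment alone can still be reported.
- Reconcile the garment table in 4.1.1 with 2.4 and 4.3.
- Reconcile the recording route in 4.6 with 15.1 and 15.6. This concerns how events are recorded, not how a subject with fever is managed.

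The cost is wording in a few sections, a correction to one risk table and one field on a form. Sample size and visits are unaffected. The downside is that the reported device-effect rate may be slightly less favourable; the component field limits this by showing which part was suspected.

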2.3 Intended Purpose

Is intended for the retention of a dressing in the axilla area.

2.4 Contraindications and Warnings

A full list of contraindications and warnings are provided in the IFU supplied with the device.

Contraindications: Known allergies to materials specified

Warnings: Do not use if you have known allergies to materials specified.

Warnings

- 1. The garment is not a wound dressing wound(s) should be fully covered by dressing(s).
- 2. If any unexpected discomfort or wound irritation occurs, please consult your doctor or nurse.
- 3. Do not use, if you have a known allergy or sensitivity to materials listed.

CE-GAX001-01

V4.0

CR: 144

Potential side effects: Dermatitis, infection and skin irritation or skin abrasion.

2.5 Summary of Required Experience/Training

[figure not shown]
The research nurse will be trained to

- Use the device and to demonstrate correct use of the device to subjects
- Determine if the subject can be included or excluded

The research nurse will train the subject:

- how to use Hidrawear AX
- how to record their temperature.

2.6 Description of Specific Procedures for the Use of the Investigational Device

2.7 Traceability

The dressing and fastener packaging will have a part number and batch number.

The Hidrawear AX garment will have a washing label with a part number.

Hidrawear AX garment packaging will have the Hidrawear AX garment lot number. The lot number will contain a unique identifier code.

CE-GAX001-01

V4.0

CR: 144

3 JUSTIFICATION FOR STUDY DESIGN

3.1 Justification for the Design of the Clinical Investigation

There is no standard of care for HS wound care globally. Subjects rely on existing non-specific wound care products. The anatomical locations of the disease are high sweat areas. The locations have hair and the skin is compromised with deep seated, painful skin lesions, tunnelling tracts and wounds. As the skin is compromised by the disease, the use of adhesive wound pads is not optimal. There is pain and discomfort involved. Subjects spend time changing dressings which has an impact on the quality aspects of their lives.[7]

The Hidrawear AX's is designed to allow quick and easy wound dressing, comfortable method of retaining the dressing that avoids use of skin damaging adhesive, resulting in better wound management that will allow the subject to have an improved quality of life.

This study will compare the product HidraWear with current methods used to manage HS wounds in the home setting. Comparison will be made:

- Between the patient's experience with existing standard dressings used on Day 0
- Between the patient's experience and the data collected in the survey

There are no studies found that capture the impact of HS wound care to the patient. This study will inform the researchers what areas of wound care should be further researched and whether quality of life is a tangible measurement in terms of HS wound care.

There is limited data available regarding the best choice of dressing in HS subjects. There is no perfect single dressing for HS and current literature suffers a lack of evidence regarding the choice of dressings in these patients.

There is a huge need for more studies evaluating topical therapies and dressings in order to improve quality of evidence and subject care. Current literature remains focused on post-surgical wound healing after an HS subject has had either minor surgery or excisional surgery [7]

Research shows that there is a significant effect on HS subjects' Quality of Life. Matusiak's literature review assesses DLQI scores from seven HS DLQI studies against studies of other dermatoses. Other dermatosis includes Skin Tumours, Atopic Dermatitis, Vascular anomalies of the face, Darier Disease, Hailey-Hailey Disease, Psoriasis, Acne Vulgaris, Alopecia and Chronic Idiopathic Urticaria. The DLQI questions the symptoms and feelings, daily activities, leisure, work or school, personal relationships and treatment of a person with HS. "The burden of disease of HS is usually greater than that reported for other common dermatoses, with mean Dermatology Life Quality Index scores indicating a moderate-to-large effect on subjects' lives." [8].

Use of the DLQI questionnaire is standard practice in the assessment of quality of life for subjects with HS. The DLQI questionnaire is a validated questionnaire. [9], [10] and [11].

Braunberger assess available dressings to HS subjects. Dressing are not specific to HS subjects. There are a range of non-active and active dressing available on the market. Braunberger 's assessment summary is "As an important component of wound healing, large, randomized controlled trials that compare dressing options for the management of wounds in hidradenitis suppurativa subjects are needed." [12]

CE-GAX001-01

V4.0

CR: 144

Hidramed's ease of use assessment and comfort is directly related to the performance of the Hidrawear AX device.

